TITLE OF THE STUDY: Surgical extrusion for the clinical crown lengthening: a 12-months prospective clinical study

RESEARCH ETHICAL COMMITTEE APROVAL DATE:
15 March 2018

PROTOCOL

1. Scientific background:

Long-term survival rates of restorations after endodontic treatment range between 81% and 100%. Outcome predictors for the restored tooth with a prosthetic crown mainly include cavity wall integrity and the presence of 1.5 to 2 mm of ferrule (360 degrees sound dentin collar). In some clinical situations, the aforementioned requirements cannot be achieved, especially in deep carious lesions, cervical perforations, crown-root fractures, and failed crowns with preexisting subgingival margins. In such cases, ferrule should not be provided at the expense of the remaining tooth structure since it may provoke a biologic width invasion and, consequently, a chronic gingival inflammation and a loss of soft tissue and bone.

Three treatment options aim to obtain adequate ferrule while respecting the biologic width: surgical crown lengthening, rapid orthodontic extrusion and surgical extrusion. Surgical crown lengthening involves the removal of hard and soft tissue for the exposure of sufficient supragingival tooth structure. Rapid orthodontic extrusion, which is a less invasive treatment, allows the preservation of periodontal tissues. However, it is necessary to consider the patient's willingness to wear orthodontic appliances, which increases the cost and time of the therapy. Surgical extrusion consists in atraumatic luxation of the tooth to enable its coronal reposition. Several authors have reported survival rates higher than 95% on surgical extrusion. However, little prospective studies are available in relation to the periodontal changes after SE.

2. Objectives:

2.1. Main objectives

- Evaluate the success rate after at least 12 months of the surgical extrusion.
- Evaluate the soft tissue rebound (STR) after at least 12 months of the surgical extrusion.

2.1. Secondary objectives

Evaluate the following periodontal and radiographic parameters:

- Gingival papillae shape and height (Jemt index).
- Bleeding on probing (mm).
- Plaque index (Turesky index).
- Gingival index (Silness & Löe index).
- Clinical attachment level (mm).
- Tooth mobility (Miller classification).
- Crown-root ratio (mm).
- Periapical healing (Rud score).
- Root resorption.
- Marginal bone loss.
- Patient satisfaction.

3. Hypotheses

Null hypothesis (H0):

H₀1: Surgical extrusion is not a predictable treatment for the restoration of single rooted teeth.

H₀2: Surgical extrusion of single rooted teeth results in an unfavorable aesthetic outcome.

Alternative hypothesis (H1):

H₁1: Surgical extrusion is a predictable treatment for the restoration of single rooted teeth.

H₁2: Surgical extrusion of single rooted teeth results in a favorable aesthetic outcome.

4. Study design

This is an interventional, monocentric, single-group, prospective clinical study.

5. Methods

5.1 Study population

This prospective study comprises 14 consecutive patients in whom 15 single-rooted teeth were surgically extruded at the Department of Endodontics at International University of Catalonia, St Cugat del Vallès, Barcelona, Spain. The sample was recruited according to the following inclusion and exclusion criteria:

Inclusion criteria:

- Systemically and periodontally healthy, non-smoking patients.
- Single-rooted, straight teeth with insufficient ferrule, which require restorative treatment.
- Teeth with a favorable crown-root ratio.

Exclusion Criteria:

- Severe systemic disease patients (American Society of Anesthesiologists classification 1 or 2).
- Multi-rooted, curved and/or short teeth.
- Teeth with an uncontrolled periodontal pathology.
- Pregnant women.
- Teeth with types II or III mobility.

All included patients signed an informed consent, and the study was approved by the Ethics Committee of Investigation of the Universitat Internacional de Catalunya (END - ECL – 2017 - 02).

5.2 Treatment plan

5.2.1 Pre-surgical assessment (Visit 1)

On the first appointment, patient's medical and dental history was reviewed. Patients age, sex and tooth number were recorded. A pre-operative cast model of each extruded tooth was taken and digitally scanned to assess the STR. Also, patient's biotype (De Rouck) was registered based on the transparency of the periodontal probe through the gingival margin while probing the buccal sulcus, as follows:

- 0: Both upper central incisors have thin biotype.
- 1: One of the two upper central incisors has a thin biotype.
- 2: Both upper central incisors have thick biotype.

A) Clinical parameters

- Percussion: assessed with a mirror handle in a vertical direction.
- Palpation: assessed by a gentle finger pressure on both buccal and palatal soft tissue around the transplant.
- Periodontal variables, using an standardized manual periodontal probe PCP-UNC 15 (Hu-Friedy®, [name]):
 - Periodontal probing depths (PPD): measured at 6 sites per tooth. Defined as the distance, in millimeters, from the gingival margin to the bottom of the probable pocket.
 - Gingival recession: measured at 6 sites per tooth. Defined as the distance, in millimeters, from the cementoenamel junction (CEJ) to the gingival margin.
 - Clinical attachment level (CAL): calculated indirectly as the sum of the previously recorded PPD and gingival recession, representing the distance between the CEJ and the bottom of the pocket on all present teeth.
 - Bleeding on probing (BoP): recorded dichotomously, at six sites, as present or absent within 15 seconds after the direct assessment of PPD, at six aspects of each tooth.
- Tooth mobility (Miller classification): measured using two dental mirror handles.
 - Grade 0: Normal (physiologic) movement when force is applied.
 - Grade 1: Mobility greater than physiologic.
 - Grade 2: Tooth can be moved up to 1mm or more in a lateral direction (buccolingual or mesiodistal). Inability to move the tooth in a vertical direction (apicocoronally).

- Grade 3: Tooth can be moved 1mm or more in a lateral direction (buccolingually or mesiodistally). Ability to move the tooth in a vertical direction.
- Gingival papillae shape and height (Jemt index): based on the distance from the highest curvature of the marginal buccal gingiva to the contact point of the transplanted tooth with the following index scores:
 - 0 No papilla is present.
 - 1 Less than half of the height of the papilla is present.
 - 2 Half or more of the height of the papilla is present but does not extend all the way up to the contact point between the teeth.
 - 3 The papilla fills up the entire proximal space and is in good harmony with the adjacent papillae. There is optimal soft tissue contour.
 - The papilla is hyperplastic and covers too much of the transplanted or adjacent tooth. The soft tissue contour is more or less irregular.
- Bleeding on probing (mm): recorded dichotomously as present or absent within 15 seconds after the assessment of PPD, at six aspects of each transplant.
- Plaque index (Turesky index): visually measured as follows:
 - 0: No plaque present
 - 1: Separate flecks of plaque at the cervical margin.
 - 2: A thin continuous back of plaque (up to 1 mm) at the cervical margin.
 - 3: A band of plaque wider than 1 mm but covering less than one-third of the surface.
 - 4: Plaque covering at least one-third but less than two-thirds of the surface.
 - 5: Plaque covering more than two-thirds of the surface.

- Gingival index (Silness & Löe index): the scores of the four areas of the tooth can be summed and divided by four to give the GI for the tooth.
 - Score 0 = Normal gingiva.
 - Score 1 = Mild inflammation - slight change in color, slight edema. No bleeding on probing.
 - Score 2 = Moderate inflammation - redness, edema, glazing. Bleeding on probing.
 - Score 3 = Severe inflammation - marked redness and edema, ulceration. Tendency toward spontaneous bleeding.

B) 2D radiographic parameters

Standardized digital bitewings and periapical radiographs with paralleling technique (Kodak RVG 6100; Carestream Health, Rochester, NY) and a selective CBCT scan (CS 9300; Carestream Health, set at 8.0 mA and 84 kV, with a 12-second exposure time and the smallest possible field of view (5 x 5 cm) were taken to assess root anatomy as well as the following radiographic parameters:

- Preoperative periapical lesion, recorded dichotomously as present or absent from the periapical radiography.
- Crown-root ratio (mm): measured on the periapical radiograph, and scored as follows:
 - Good: crown-root ratio < 1.
 - Just: crown-root ratio = 1.
 - Unfavorable: crown-root ratio > 1.
- Marginal bone loss: based on the bone crest aspect on the bitewing radiograph, as follows:
 - Initial: < 25% of marginal bone loss.
 - Moderate: between 25% - 50% of marginal bone loss.
 - Severe: > 50% of marginal bone loss.

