5.2.2 Surgical extrusion (Visit 2)

The principal investigator performed all the procedures following the modified technique described by Kahnberg. Under local anesthesia and after having removed the caries lesion, each tooth was gently luxated with thin elevators, which were placed no more than 1mm within the gingival margin to avoid damaging the cervical PDL cells. Subsequently, teeth were coronally positioned using thin forceps to expose sufficient supracrestal tooth structure and splinted for 4 weeks with a retainer. Post surgery, the patients were prescribed analgesics and antibiotics for 1 week, and instructed to rinse daily with 0.12% chlorhexidine and follow a soft diet for 2 weeks.

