5.2.5 Post-surgical assessment (Visit 5)

Patients were recalled at 12 months post-surgery, when a cast model was taken for the post-operative digital scanning, and the following clinical and radiographic parameters were recorded:

A) Clinical parameters

- Percussion.
- Palpation.
- Periodontal probing depths.
- Gingival recession.

- Clinical attachment level.
- Bleeding on probing.
- Tooth mobility.
- Gingival papillae shape and height.
- Bleeding on probing.
- Plaque index.
- Gingival index.
- Soft tissue rebound (STR): measured in mm by superposing both pre-operative and post-operative scanned models of each patient using surgical planning software (Blue Sky Plan, Blue Sky Bio, Libertyville, IL, USA). Soft tissue rebound was measured by calculating the difference between the lowest point of the gingival margin of the pre-operative model and the lowest point of the gingival margin of the post-operative model.

B) Radiographic parameters

- Periapical healing (Rud score): based on any radiolucency surrounding the apical third of the root, as follows:
 - Complete: Reestablishment of the periodontal space and the hard lamina around the apex.
 - Incomplete (scar tissue): Decrease or alteration of the apical lesion with at least one of the following characteristics: the periphery of the radiolucency is irregular and may be demarcated by a compact bony margin; the radiolucency is located asymmetrically around the apex.
 - Uncertain: Radiolucency greater than twice the width of the periodontal space and surrounded by tissue resembling a hard lamina. Lesion with circular or semicircular periphery and located symmetrically around the apex.
 - Unsatisfactory: Increase or maintenance of the size of the lesion.

- Root resorption: based on the aspect of the transplant periodontal ligament, as follows:
 - Absence of root resorption: complete PDL healing with normal width of the PDL space around the whole root.
 - Inflammatory root resorption: radiolucency is observed all along the external root surface of the dentin.
 - Replacement resorption: resorption lacunae are filled with bone and the PDL space is missing.
- Crown-root ratio (mm).
- Marginal bone loss.

C) Patient's satisfaction

Each patient filled in a questionnaire based on a 10-cm visual analogue scale to assess their degree of satisfaction regarding the surgical procedure and the esthetic outcome; 0 indicated a complete satisfaction while 10 was entirely unsatisfactory.

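### The crown-root ratio is scored on a near-binary scale with no within-tooth change planned, so worsening that stays below 1 is scored as no change

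*Combined protocol and SAP*

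**What the plan says.** The crown-root ratio is one of the secondary parameters in section 2. Section 5.2.1, under the 2D radiographic parameters, defines it: "Crown-root ratio (mm): measured on the periapical radiograph, and scored as follows". The classes are "Good: crown-root ratio < 1", "Just: crown-root ratio = 1" and "Unfavorable: crown-root ratio > 1".

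Section 5.1 admits "Teeth with a favorable crown-root ratio" and gives no numeric limit. It also excludes "Multi-rooted, curved and/or short teeth", again without a length. Section 5.2.2 describes the procedure without a distance in millimetres: "teeth were coronally positioned using thin forceps to expose sufficient supracrestal tooth structure".

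The second reading falls at Visit 5 (section 5.2.5: "Patients were recalled at 12 months post-surgery"). The parameter is listed there again with no new definition, so the Visit 1 scoring carries over.

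The SAP summarises every variable descriptively, by means and percentages. It does not say which summary applies to the crown-root ratio. The only comparison before and after surgery that it names is for marginal bone loss. The ratio is not among the success criteria.

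**The concern.** Moving a tooth coronally takes root out of the bone, so a less favourable crown-root ratio is a direct mechanical consequence of the procedure. The ratio is a natural place to look for that consequence. The extrusion distance is not listed as a recorded variable, and the success criteria do not use the ratio.

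The scale handles this poorly in two ways. The middle class is a single point, which a continuous measurement almost never hits, so the score is in effect below 1 versus above 1. A real worsening on the lower side of 1 then leaves the score unchanged, while a trivial difference around 1 can move a tooth from the best class to the worst. If only the classes are reported, the size of the change in root support is lost, although it was measured. What is at stake is how a descriptive secondary result is read, not the main objectives.

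**Working it through.** **Plan's own figure.** There is none for the crown-root ratio. The one design calculation, the sample size, rests on soft tissue rebound and has no bearing here.

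**Inputs.** The class limits come from section 5.2.1. The documents give no crown length, root length, baseline ratio or extrusion distance, so every length below is an assumption.

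**Formulas.** Let C be the crown part above bone, R the root in bone and e the extrusion, all in mm. The baseline ratio is C/R. At 12 months there are two simple cases:

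- Case A, crown height above bone kept: C/(R − e). The tooth leaves the class below 1 when e ≥ R − C.
- Case B, crown part lengthened by e: (C + e)/(R − e). The tooth leaves that class when e ≥ (R − C)/2.

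The documents do not say which case applies. They do not define how the crown part is delimited, and at Visit 5 it belongs to a restored tooth.

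**Single teeth.**

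| Assumed C, R, e (mm) | Baseline | Case A | Case B |
|---|---|---|---|
| 8, 14, 3 | 8/14 = 0.57 | 8/11 = 0.73, same class | 11/11 = 1.00, changes |
| 9, 13, 3 | 9/13 = 0.69 | 9/10 = 0.90, same class | 12/10 = 1.20, changes |
| 7.8, 13, 3 | 0.60 | 7.8/10 = 0.78, same class | 10.8/10 = 1.08, changes |
| 10.4, 13, 2 | 0.80 | 10.4/11 = 0.95, same class | 12.4/11 = 1.13, changes |
| 11.7, 13, 2 | 0.90 | 11.7/11 = 1.06, changes | 13.7/11 = 1.25, changes |

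In case A the first two teeth worsen by 27% (0.727/0.571 = 1.27) and 30% (0.900/0.692 = 1.30), and the score does not move.

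**Share of teeth changing class.** Assume baselines spread evenly over an interval, R between 11 and 15 mm, and e = 2 mm. A tooth changes class if its baseline is at least 1 − e/R (case A) or 1 − 2e/R (case B).

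| Baseline interval | Case A | Case B |
|---|---|---|
| 0.5 to 0.8 | 0% | 22–55% |
| 0.5 to 1.0 | 27–36% | 53–73% |
| 0.8 to 1.0 | 67–91% | 100% |

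The same 2 mm of extrusion can therefore register in none of the teeth or in all of them, depending on inputs that the documents do not give.

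**Reading error.** For an assumed tooth with both parts 13 mm, a crown reading of 12.9 mm gives 12.9/13 = 0.992 (best class). A reading of 13.1 mm gives 13.1/13 = 1.008 (worst class). A difference of 0.2 mm spans the whole scale.

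**Precision of a class count.** If none of 15 teeth changed class, the exact two-sided 95% upper limit would be 1 − 0.025^(1/15) = 0.218, about 22%. This treats the 15 teeth, from 14 patients, as independent.

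**The case against.** Four points on the other side carry weight.

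- **The number may be kept.** The protocol has the ratio measured before it is scored and nowhere says that the measurement is discarded. The SAP allows for means as well as percentages. This stands: loss of information is a risk of an unclear plan, not an established fact. But even if mean ratios were given for the same teeth at both visits, a reader could recover the mean change and not its SD or confidence interval.
- **There is no ceiling in the direction that matters.** A reader might infer that, because only favourable teeth are enrolled, all start in the best class and the cost of extrusion is mostly hidden. The documents do not support that. *Favorable* is not a class of the scale and could include a ratio of 1, from which any worsening would show. Two worse classes lie in the direction in which extrusion pushes the ratio. In case B both leading examples change class. Even in case A, 4 mm of extrusion takes the second to 9/9 = 1.00.
- **Other variables also bear on support.** Mobility, probing depth, attachment level and marginal bone loss are recorded at both visits, and several enter the success criteria. This stands, and it limits the consequence.
- **The ratio is a minor variable.** It has no planned test and plays no part in the success definition or the sample size. This also stands.

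None of these points answers the narrow one: the only output specified for this variable is a near-binary score, and no paired change is planned.

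**Conclusion.** The point holds in a limited form. As written, the scoring records any worsening that stays below 1 as no change, and it makes teeth close to 1 sensitive to small reading differences. The SAP plans no within-tooth change that would make up for this.

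The frequency of the problem is unknown. Under the assumptions tried for 2 mm of extrusion, the share of teeth that would change class runs from 0% to 100%. That range supports neither a claim that the worsening is mostly missed nor one that it is mostly seen. The conclusion rests only on the class limits, on the lack of another definition at Visit 5 and on the SAP's silence about paired change. The assumed lengths serve as illustration.

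It concerns a descriptive secondary parameter. Neither the success rate nor the soft tissue rebound result depends on it. It is worth correcting because the better summary uses measurements that the scoring already requires.

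**What to change.** - Keep the measured crown and root lengths in mm for each tooth, and state how the two parts are delimited on the radiograph at both visits.
- In the SAP, report the numeric ratio at Visits 1 and 5 and the paired within-tooth change with its SD and 95% CI.
- Show the three classes only as a secondary shift table, Visit 1 against Visit 5.
- As a clarification only, the sponsor should state what *favorable* in section 5.1 meant on this same ratio. Section 5.1 describes teeth already treated, so this documents the limit that was used and does not alter who was enrolled.

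The cost is a few lines of SAP wording if the measurements were stored. If only the classes were stored, the existing radiographs from the two visits would have to be re-read for 15 teeth. No new visit or examination is needed.

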5.2 Success assessment

The following criteria were evaluated to establish the success of the treatment:

- Normal function of the extruded tooth with physiologic mobility without pain or discomfort.
- Healthy periodontal tissue surrounding the extruded tooth with periodontal pockets < 4 mm.
- Normal appearance of the PDL around the extruded tooth with no signs of any progressive root resorption or marginal bone loss $> 25\%$.

STATISTIC ANALYSIS PLAN (SAP)

The sample size was calculated based on the STR variation, using as a reference the study of Arora et al., in which the mean STR reported at 6 months was 0.77 ± 0.58 mm after the crown lengthening. This measure corresponds to a large effect size ($d=1.3$). In the present study the sample size was calculated using one sample t-test, considering a relevant STR of 0.5 mm at 12 months and a dropout of 15%. Thus, the final sample consisted in 15 patients, for a power of 80%, and considering an effect size of $d = 0.85$.

The data contained in the follow-ups were entered into a database (Excel, Microsoft Corporation) for data analysis and preparation for the final report. All the variables were analyzed using a descriptive method (mean, %). Besides, Chi² test was used to find a statistical relation between pre-operative and post-operative marginal bone loss of the extruded teeth.

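### The three bone-loss classes hide any change below 25%, and an ordinary Chi² on the same 15 teeth tests association or ignores the pairing, with little power for modest change across 25%

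*Combined protocol and SAP*

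**What the plan says.** Section 5.2.1, part B, grades marginal bone loss from the bitewing in three classes: "Initial: < 25% of marginal bone loss", "Moderate: between 25% - 50% of marginal bone loss" and "Severe: > 50% of marginal bone loss". There is no class for no loss, and no reading in mm or as a percentage is planned. Section 5.2.5 records the parameter again at 12 months.

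The last paragraph of the SAP describes all variables by means and percentages and adds one test: "Chi² test was used to find a statistical relation between pre-operative and post-operative marginal bone loss of the extruded teeth". No other test of an outcome is named; the one-sample t-test appears only in the sample-size calculation for soft tissue rebound.

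Section 5.1 admits "Systemically and periodontally healthy, non-smoking patients" and excludes "Teeth with an uncontrolled periodontal pathology". It sets no limit on bone loss and gives no baseline distribution. The sample is "14 consecutive patients in whom 15 single-rooted teeth were surgically extruded". The success definition also uses a 25% limit: a successful tooth has "no signs of any progressive root resorption or marginal bone loss" above 25%.

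**The concern.** Three features combine badly. The lowest class is wide, eligibility favours teeth that start in it, and the chosen test is not built for two measurements on the same tooth. A tooth can lose nearly a quarter of its marginal bone and be recorded as unchanged. The Chi² result could then be uncomputable, non-significant for lack of sensitivity, or significant without any change. Marginal bone loss is a listed secondary objective and this is the only outcome test in the SAP, so a reader could easily take its p-value as evidence about bone stability after extrusion.

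**Working it through.** **Inputs.** From the documents: 15 teeth in 14 patients (section 5.1), class limits at 25% and 50% (section 5.2.1), Chi² test (SAP). The SAP gives no significance level; 0.05 two-sided is assumed. The teeth are treated as independent of one another, although one patient contributes two.

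**The plan's own figure.** The stated 15 belongs to soft tissue rebound. A one-sample t-test at d = 0.85 needs 13 for 80% power, and 13 × 1.15 = 14.95, or 15 (dividing by 0.85 gives 15.3, or 16). The stated number is thus reproduced, but it says nothing about the bone-loss test, for which no power is given.

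**Reading A: pre-by-post cross-table.** If all 15 teeth start as Initial, the table has one row and Chi² is undefined. With 14 Initial and 1 Moderate and no tooth changing:

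χ² = N(ad − bc)² / (product of the four margins) = 15 × 14² / (14 × 1 × 14 × 1) = 15.0, p = 0.0001.

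The smallest expected count is 1 × 1/15 = 0.07, and Fisher's exact p is 1/15 = 0.067. The small Pearson p shows only that the grade before surgery predicts the grade after it.

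**Reading B: class proportions before against after.** With all 15 teeth Initial before surgery and k teeth at 25% or more after it, the uncorrected statistic reduces to χ² = 30k/(30 − k).

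| Teeth crossing 25% | χ² | Pearson p | Fisher p | Exact McNemar p (2 × 0.5^k) |
|---|---|---|---|---|
| 3 | 3.33 | 0.068 | 0.224 | 0.250 |
| 4 | 4.62 | 0.032 | 0.100 | 0.125 |
| 5 | 6.00 | 0.014 | 0.042 | 0.063 |
| 6 | 7.50 | 0.006 | 0.017 | 0.031 |

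Pearson therefore needs 4 of 15, while treating 15 teeth measured twice as 30 independent teeth. The exact paired test needs 6. Power is the binomial probability of reaching that count:

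| Assumed true crossing rate | Pearson (4 or more) | Exact McNemar (6 or more) |
|---|---|---|
| 10% | 6% | 0.2% |
| 20% | 35% | 6% |
| 30% | 70% | 28% |
| 40% | 91% | 60% |

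**Cost of the classes against a number.** Assume normal baseline loss with mean 8% and SD 4, and an independent change with mean m and SD s. The chance that a tooth reaches 25% is p = 1 − Φ((25 − 8 − m)/√(4² + s²)). The chance that none of the 15 does is (1 − p)^15. The paired t-test has noncentrality √15 × m/s on 14 degrees of freedom.

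| Mean increase (SD), points | p per tooth | No tooth crosses | Pearson power | Paired t-test power |
|---|---|---|---|---|
| 5 (5) | 1 − Φ(12/6.40) = 0.030 | 63% | 0.1% | 95% |
| 8 (6) | 1 − Φ(9/7.21) = 0.106 | 19% | 7% | over 99% |
| 15 (8) | 1 − Φ(2/8.94) = 0.412 | under 0.1% | 92% | over 99% |

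The baseline and change values are assumptions, since the documents give none. The t-test column also assumes readings without error.

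**The case against.** A reader might infer that the test cannot detect change at all or is almost certain to show nothing. The documents do not support that. Under reading B, Pearson's test is significant once 4 of 15 teeth cross 25%, and it has good power for large losses. Under reading A it can be significant with no change at all.

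A reader might also take it as established that nearly all teeth start as Initial. Section 5.1 makes this likely, but it excludes only uncontrolled pathology, and the background section describes target teeth (deep caries, root fractures, failed subgingival crowns) in which local bone loss is possible. If each tooth had a 90%, 95% or 99% chance of being Initial (assumed), at least 14 of 15 would be so with probability 55%, 83% or 99%.

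Quoting the exact McNemar test at the 8-point increase, about 0.3% power, would overstate the loss, because the SAP does not plan that test.

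Other points stand in part. The 25% limit matches the success criterion, so the classes serve that purpose. Class counts will be described whatever the test shows, and attachment level in mm gives finer, though not radiographic, information. Bone loss is one of eleven secondary parameters.

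The most serious objection concerns the remedy. Section 5.2.2 moves the tooth coronally, section 5.2.4 prepares it for a crown, and no reference point for bone loss is given. A numeric change read from a landmark on the extruded tooth could count the intended displacement as bone loss. That objection is correct, and the fix has to meet it. None of these points makes the Chi² test suitable.

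**Conclusion.** The point holds in a limited form. The recorded scale cannot show change within 0–25%, and the planned test is wrong for paired grades under either reading: as a cross-table it tests association and may be undefined, and as a marginal comparison it ignores the pairing. For modest change across 25% its power is low, about 6% at a 10% crossing rate and 35% at 20%; for large change it is adequate. On the assumed baseline, power runs from 0.1% to 92% as the mean increase goes from 5 to 15 points, against about 95% or more for error-free numeric readings. These sizes rest on all teeth starting as Initial, a 0.05 level and assumed distributions. The invisibility of change below 25% and the mismatch between test and question rest on the documents alone. The plan should be changed, but this concerns a secondary outcome, not the two main objectives.

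**What to change.** Drop the Chi² test. Read marginal bone level as a number, in mm or percent, on the standardized radiographs for Visits 1 and 5. Report the mean paired change with a 95% CI, using a paired t-test or the Wilcoxon signed-rank test. Keep the three classes as descriptive counts and for the success criterion on loss above 25%.

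State the reference point for the reading. It should be independent of the extruded tooth, for example a landmark on an adjacent tooth on the same film; otherwise the analysis must account for the planned displacement.

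The cost is a revised SAP sentence, a short definition of the measurement, and numeric readings on about 15 pairs of films already in the plan, with some measurement error. No extra visit or exposure is needed.
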